## 9.5 EQ-5D-3L questionnaire and scoring information

By placing a tick in one box in each group below, please indicate which statements best describe your own health state today.

### Mobility

- I have no problems in walking about
- I have some problems in walking about
- I am confined to bed

### Self-Care

- I have no problems with self-care
- I have some problems washing or dressing myself
- I am unable to wash or dress myself

### Usual Activities (e.g. work, study, housework, family or leisure activities)

- I have no problems with performing my usual activities
- I have some problems with performing my usual activities
- I am unable to perform my usual activities

### Pain/Discomfort

- I have no pain or discomfort
- I have moderate pain or discomfort
- I have extreme pain or discomfort

### Anxiety/Depression

- I am not anxious or depressed
- I am moderately anxious or depressed
- I am extremely anxious or depressed

Values for the 243 health states defined by the EuroQol classification have been calculated using a regression model. The following worked example indicates how these coefficients are to be used so as to compute the estimated values for each state.

**Calculating EQ-5D-3L state scores - a worked example**

EuroQol dimension	Level 2	Level 3
Mobility	0.069	0.314
Self-care	0.104	0.214
Usual activity	0.036	0.094
Pain / discomfort	0.123	0.386
Anxiety / depression	0.071	0.236
	Constant = 0.081	N3 = 0.269

The arithmetic needed to recover the estimated value for any health state from this table of decrements is given by the following example:

- Taking health state 1 1 2 2 3
- Full health (1 1 1 1 1) = 1.0
- Constant term (for any dysfunctional state)(subtract 0.081)
- Mobility. level 1 (subtract 0)
- Self-care. level 1 (subtract 0)
- Usual activity. level 2 (subtract 0.036)
- Pain / discomfort. level 2 (subtract 0.123)
- Anxiety / depression. level 3 (subtract 0.236)
- Level 3 occurs within at least 1 dimension (subtract N3 parameter 0.269)
- Hence the estimated value for state 1 1 2 2 3 is given by  
 $1.0 - 0.081 - 0.036 - 0.123 - 0.236 - 0.269 = .25$

**9.6 Prohibited medication: metastasis-free survival**

Following medications considered prohibited was selected in CM dataset:

- Radiopharmaceuticals (ATC codes V10BX, V10XX03),
- Immunotherapy (e.g. sipuleul T) (ATC code L03),
- Cytotoxic chemotherapy and any other systemic antineoplastic therapy (ATC code class L: antineoplastic and immunodulating agents , with the exception of L02AE (Gonadotropin-releasing hormone analogues)),
- Enzalutamide, ARN-509, bicalutamide, flutamide, nilutamide (ATC code L02B),
- Cyproterone acetate estrogen (ATC codes G03H, G03C),
- 5  $\alpha$ -reductase inhibitor (ATC code G04CB),
- Abiraterone acetate, TAK-700 or other CYP17 inhibitors (ATC code L02B),
- Systemic ketoconazole (as antineoplastic therapy) (ATC codes D01AC08; G01AF11, J02AB02),
- Osteoclast-targeted therapy such as bisphosphonate or denosumab (ATC code M05B) given for preventing skeletal-related events. These drugs are allowed for treatment of osteoporosis,
- Continuous use of systemic corticosteroid (ATC code H02).

Sponsor's assessment of prohibited medication is presented in a supplementary document.

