4.2 Inclusion criteria

To be included in the study, patients must meet all of the following criteria:

1. Written informed consent (IC) obtained.
2. Males aged ≥ 18 years.
3. Histologically or cytologically confirmed adenocarcinoma of prostate without neuroendocrine differentiation or small cell features.
4. CRPC defined as 3 rising PSA levels after the nadir taken at least 1 week apart during ADT. If the patient has a history of antiandrogen use, the most recent PSA value must be obtained at least 4 weeks after antiandrogen withdrawal. See Section 0 for further details.
5. Castrate level of serum testosterone (< 1.7 nmol/l [50 ng/dl]) on GnRH agonist or antagonist therapy or after bilateral orchiectomy. Patients who have not undergone bilateral orchiectomy must continue GnRH therapy during the study.
6. PSADT of ≤ 10 months and PSA ≥ 2 ng/ml at screening. See Section 0 for further details.
7. Eastern Cooperative Oncology Group (ECOG) performance status of 0-1.
8. Blood counts at screening: haemoglobin ≥ 9.0 g/dl, absolute neutrophil count $\geq 1500/\mu\text{l}$ ($1.5 \times 10^9/\text{l}$), platelet count $\geq 100,000/\mu\text{l}$ ($100 \times 10^9/\text{l}$) (patient must not have received any growth factor or blood transfusion within 7 days of the haematology laboratory obtained at screening).

9. Screening values of serum alanine aminotransferase (ALT) and aspartate transaminase (AST) ≤ 2.5 x upper limit of normal (ULN), total bilirubin ≤ 1.5 x ULN (except patients with a diagnosis of Gilbert's disease), creatinine ≤ 2.0 x ULN.
10. Sexually active patients, unless surgically sterile, must agree to use condoms as an effective barrier method and refrain from sperm donation during the study treatment and for 3 months after the end of the study treatment.

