5.7 Prior, concomitant and follow-up treatments

5.7.1 Prior and concomitant treatments

History of all prostate cancer treatments, including radiotherapy, before the time of IC must be recorded on the CRFs.

All concomitant treatments from the time of IC until the end-of-study treatment visit must be recorded on the CRFs. Contrast media do not need to be recorded as concomitant medication unless there is an adverse event related to its administration (e.g. allergic reaction). Once the patient has been withdrawn from study treatment, follow-up treatments will be recorded if used to treat new related or unresolved related AEs or if it is a systemic antineoplastic therapy.

Patients who have not undergone bilateral orchiectomy must continue GnRH agonist or antagonist therapy during the study.

The patient must not have been administered another investigational drug within 28 days before randomisation.

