### 6.1.2 Demographic and Baseline Characteristics

Descriptive summaries of demographics and baseline characteristics will be presented by treatment group and overall for the FAS and SAF populations. Comparability of the treatment groups with respect to demographics and baseline characteristics will be assessed using descriptive summaries.

The following demographic data will be summarized:

- Age (years), calculated at the date of randomization using date of birth
- Age (years) (<65, 65 - 74, 75 - 84, ≥85)
- Sex (Male)
- Race (White, Asian, Black or African American, Other)
- Ethnicity (Hispanic or Latino)
- Height (cm)
- Weight (kg)
- Body Mass Index (BMI) (kg/cm^2) (< 20, 20 to < 25, 25 to < 30, ≥ 30)
- Geographical region (North America, Asia Pacific, ROW).

The following baseline characteristics will be summarized:

- PSADT (≤6, >6 months) - IVRS
- PSADT (≤6, >6 months) - CRF
- PSADT (months)
- Osteoclast-Targeted Therapy (yes, no) - IVRS
- Osteoclast-Targeted Therapy (yes, no) - CRF
- ECOG Performance status
- Gleason Score
- Primary tumor classification
- Regional lymph node classification
- Time since start of castration-resistant (months)
- Time since initial diagnosis (capture under clinical staging) (months)

- Time from start of first prior GnRH agonist/antagonist to start of study-drug (months) (for selection, see 9.12)
- Time from prior orchiectomy to start of study-drug (months)
- Time from start of first prior antiandrogen (AR inhibitors) to start of study-drug (months) (for selection, see 9.11)
- Time from the first prior ADT to start of study drug (months) (ADT is defined by GnRH agonist/antagonist, orchiectomy, antiandrogen (AR inhibitors))
- Renal function - eGFR at baseline:
  - Normal:  $eGFR \geq 90$  mL/min
  - Mildly impaired:  $60 \leq eGFR < 90$  mL/min
  - Moderately impaired:  $30 \leq eGFR < 60$  mL/min
  - Severely impaired:  $15 \leq eGFR < 30$  mL/min
  - End stage renal disease:  $eGFR < 15$  mL/min and not on dialysis, or requiring dialysis

eGFR will be calculated according to the Modification of Diet in Renal Disease (MDRD) Formula:

$$eGFR \text{ (mL/min/1.73m}^2\text{)} = 186 \times SCR^{-1.154} \times \text{age}^{-0.203} \times (0.742, \text{ if female}) \times (1.212 \text{ if blacks or African American}) \times (0.881 \text{ if Japanese}) \times (1.227 \text{ for Chinese (mainland China, Taiwan and Hongkong), where SCR= serum creatinine measured in mg/dL}$$

- Hepatic impairment at baseline:

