## 9.12 GnRH agonist/antagonist therapy

The GnRH antagonist treatments were selected in CM dataset (ATC code starting with L02AE, H01CA and L02BX).

L02AE Gonadotropin releasing hormone analogues (L02AE01 buserelin, L02AE02 leuprorelin, L02AE03 goserelin, L02AE04 triptorelin, L02AE05 histrelin), H01CA Gonadotropin releasing hormones, L02BX Other hormone antagonists and related agents (L02BX01 abarelix, L02BX02 degarelix, L02BX03 abiraterone (except if used as previous therapy)).

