## 9.13 Hormonal therapy

Hormonal therapy will be were selected in CM dataset:

The GnRH antagonist treatments (ATC code starting with L02AE, H01CA and L02BX).

L02AE Gonadotropin releasing hormone analogues (L02AE01 buserelin, L02AE02 leuprorelin, L02AE03 goserelin, L02AE04 triptorelin, L02AE05 histrelin), H01CA Gonadotropin releasing hormones, L02BX Other hormone antagonists and related agents (L02BX01 abarelix, L02BX02 degarelix, L02BX03 abiraterone (except if used as previous therapy)).

The antiandrogen (AR inhibitors) therapy treatments (ATC code starting with L02BB and G03HA01).

L02BB antiandrogens (L02BB01 flutamide, L02BB02 nilutamide, L02BB03 bicalutamide, L02BB04 enzalutamide), G03HA antiandrogens plain (G03HA01 cyproterone).

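### SAP 9.6 exempts GnRH agonists but not the antagonists abarelix and degarelix from the prohibited-drug list that drives MFS censoring

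*SAP*

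**What the plan says.** SAP 9.6 lists, by ATC code, the medications treated as prohibited for MFS. The entry for cytotoxic and other systemic antineoplastic drugs takes the whole of class L "with the exception of L02AE (Gonadotropin-releasing hormone analogues"). Two further entries carry the code L02B: one names enzalutamide and other antiandrogens, the other abiraterone and other CYP17 inhibitors. The section closes by saying that the sponsor's "assessment of prohibited medication is presented in a supplementary document".

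Elsewhere the SAP classifies GnRH drugs more widely. Section 9.12 lists "L02BX01 abarelix, L02BX02 degarelix" as GnRH therapy. Section 9.13 describes "The GnRH antagonist treatments (ATC code starting with L02AE, H01CA and L02BX"). Section 6.1.2 says "ADT is defined by GnRH agonist/antagonist, orchiectomy, antiandrogen (AR inhibitors").

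In Protocol 4.2, inclusion criterion 5 requires castrate testosterone "on GnRH agonist or antagonist therapy or after bilateral orchiectomy" and adds: "Patients who have not undergone bilateral orchiectomy must continue GnRH therapy during the study". Protocol 5.7.1 says: "Patients who have not undergone bilateral orchiectomy must continue GnRH agonist or antagonist therapy during the study".

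Starting a prohibited new anticancer treatment before documented metastasis has these consequences:
- **Tables 2, 3 and 14** (primary MFS, sensitivity analysis 1, PFS): censored at the last scan before the start.
- **Table 4** (sensitivity analysis 2): an event on the start date.

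**The concern.** The L02AE exemption shows that GnRH therapy was meant to stay off the prohibited list. As coded, it covers the agonists only. The antagonists are in class L but not in L02AE, so the list selects them. Nothing in either document gives a reason to separate the two groups.

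The list decides whether a patient is censored, has an event or stays at risk in the primary endpoint. A patient who changes from an agonist to an antagonist during the study would leave the primary risk set at his previous scan, and any later metastasis or death would not count. In sensitivity analysis 2, which is there to test the censoring rule, the same change of background therapy would be recorded as an MFS event.

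**Working it through.** **Step 1: apply the SAP 9.6 codes to the drugs named in SAP 9.11 to 9.13.**

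| Drug | Code | Class L except L02AE | L02B (two entries) |
|---|---|---|---|
| Agonists (buserelin to histrelin) | L02AE01–05 | no | no |
| Other GnRH | H01CA | no | no |
| Abarelix | L02BX01 | yes | yes, if applied as a code |
| Degarelix | L02BX02 | yes | yes, if applied as a code |
| Abiraterone | L02BX03 | yes (intended) | yes (intended) |

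The class L entry alone selects both antagonists. Widening that exemption alone would leave both selected through L02B wherever those entries are run as codes.

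**Step 2: is an exemption intended?** Current Protocol 5.7.2 bars starting other systemic antineoplastic therapy and states no GnRH exception. The Amendment 4 log records that a sentence excepting GnRH was removed only as redundant. SAP v4.2 (September 2018) predates that amendment (July 2019). The log is cited for intent only, not as an error. If 5.7.2 were instead read as barring any new GnRH drug, agonist starts would be flagged too, and SAP 9.6 exempts those. The asymmetry remains on either reading.

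**Step 3: the plan's own design figures.** With 385 events, 2:1 allocation and hazard ratio (HR) 0.71, the Freedman formula gives

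z = √(385 × 2) × (1 − 0.71) / (1 + 2 × 0.71) − 1.96 = 3.325 − 1.96 = 1.365,

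that is, 91.4% power against the stated 91%. (Schoenfeld's formula gives 88.6%.) Treating 5% × 1500 = 75 baseline events as non-informative gives a diluted HR of 0.65^(310/385) = 0.707, matching the stated 0.71.

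**Step 4: size of the effect.** The documents do not say how many patients newly start an antagonist, so the share is assumed. The simulation used 5000 trials per setting.
- From SAP 3.1: 1500 patients 2:1, 40 months' accrual (taken as uniform), placebo median 25 months, HR 0.65, 5% baseline-metastasis events at randomisation, cut-off at the 385th counted event.
- Assumed: 40% dropout reached at 24 or at 40 months; flagging equal by arm and unrelated to prognosis; unstratified log-rank and Cox. A flagged patient is censored at the last 16-weekly scan (primary) or has an event at the start date (sensitivity analysis 2, SA2).

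Ranges cover the two dropout readings. *Spread* means starts uniform over months 0–24. *Immediate* means all starts directly after randomisation, an upper bound.

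| Share flagged (patients) | Hidden true events, primary: spread / immediate | False events, SA2: spread / immediate | SA2 HR: spread / immediate |
|---|---|---|---|
| 0.2% (3) | 0.24–0.25 / 0.64 | 1.2 / 2.5–2.6 | 0.700–0.702 / 0.700–0.702 |
| 0.5% (8) | 0.64–0.66 / 1.7 | 3.2 / 6.6–7.0 | 0.702–0.703 / 0.704–0.706 |
| 1% (15) | 1.2 / 3.1–3.2 | 5.9–6.0 / 12.5–13.0 | 0.703 / 0.707–0.712 |
| 2% (30) | 2.4–2.5 / 6.4–6.5 | 11.9–12.0 / 25.1–26.2 | 0.706–0.710 / 0.714–0.717 |
| 5% (75) | 6.1–6.4 / 16.6–16.7 | 29.9–30.4 / 63.8–66.8 | 0.718–0.721 / 0.735–0.739 |

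Without flagging the HR is 0.698–0.704 across settings. With flagging the primary HR changes by at most 0.002 and primary power by at most 0.4 points (all runs 91.8–93.2%). The 385-event cut-off moves by at most 1.05 months. SA2 power is 91.2–92.8% at 1% flagged and 88.2–90.1% at 5%.

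**The case against.** **The list may be only a first pass.** SAP 9.6 qualifies some entries by indication or duration (ketoconazole, osteoclast-targeted drugs, corticosteroids), which no ATC code carries. The codes may therefore only pull candidates for the sponsor to adjudicate, as in 9.7, 9.8 and 9.10. If so, selecting an antagonist is over-capture that adjudication may correct. This stands as a condition on the MFS consequence. It does not make the written rule right: the SAP gives the assessment no criteria and no precedence over the codes.

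**The table rows say *anticancer*.** A switch between GnRH drugs could be read as continued background therapy and not as a new anticancer treatment. That reading is possible, but the word itself does not exclude an antagonist. SAP 9.13 lists these drugs as hormonal therapy, although it does so to define a baseline characteristic, and SAP 9.6 files class L under antineoplastic therapy.

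**Few patients may be involved.** Only new starts after randomisation and before metastasis count, and the documents do not show that even one occurred. The assumed shares have no source, and the largest shift needs 5% flagged immediately after randomisation. All of this stands, and it is why the point is minor.

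**It is late to edit the list.** The SAP supplement for the final report addendum displays patients who crossed over from placebo to darolutamide, so unblinding appears to have passed. That also stands, and it shifts the remedy to a count.

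**Conclusion.** The point holds as a minor error in the written rule. SAP 9.6 exempts GnRH agonists and selects the antagonists abarelix and degarelix, although both documents otherwise treat the two groups alike. Whether any patient was misclassified depends on the unseen sponsor's assessment and on the number of new antagonist starts, and neither can be determined from the documents.

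Under the stated assumptions, each 10 patients wrongly flagged hide about 0.8 true events in primary MFS (upper bound about 2.2) and add about 4 to 9 false events to sensitivity analysis 2. The primary result is essentially unchanged at every rate tried. The sensitivity analysis 2 hazard ratio stays at 0.70–0.71 up to 1% flagged and reaches 0.72–0.74 at 5%. These figures assume equal, non-informative flagging, and no direction of bias is claimed.

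**What to change.** In SAP 9.6, exempt L02BX01 and L02BX02 by drug from the class L entry and from both L02B entries, and keep abiraterone (L02BX03) selected. Apply the corrected list to Tables 2, 3, 4 and 14.

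If unblinding has passed, report the number of patients flagged only by these two codes. If it is not zero, rerun MFS and sensitivity analysis 2 with the corrected list as a documented sensitivity analysis.

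Separately, the prohibited list in SAP 6.2.1.1 and 9.6 differs from Protocol 5.7.2 on the corticosteroid dose threshold, the osteoclast-therapy allowance and investigational products. These passages must be reconciled. The *anticancer* wording may keep the first two differences from reaching MFS.

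The cost is two drug codes and some aligned wording, with no new data. After unblinding it is one count and, only if needed, one rerun of two analyses.

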### 9.7 Cytotoxic chemotherapy: time to cytotoxic chemotherapy

The cytotoxic chemotherapy was selected in CM dataset (ATC code L01A, L01B, L01C, L01D, and L01X). ). Sponsor's assessment of cytotoxic chemotherapy is presented in a supplementary document.

### 9.8 Antineoplastic therapy: time to initiation of subsequent antineoplastic therapy

- Antineoplastic therapy treatment was selected in CM dataset
- ATC code class L (antineoplastic and immunodulating agents): L01 Antineoplastic agents (except cytotoxic chemotherapy L01A, L01B, L01C, L01D and L01X), L02 endocrine therapy and L03 immunostimulants
- ATC code class H: H02Corticosteroids for systemic use.

Sponsor's assessment of antineoplastic therapy is presented in a supplementary document.

## 9.9 Statins medications

Statins will be identified using the Standardized Drug Grouping (SDG) classification 'Statins'.

## 9.10 Opioid for cancer pain

The opioid treatments were selected in CM dataset (ATC code starting with N02A). Sponsor's assessment of opioid treatments is presented in a supplementary document.

## 9.11 Antiandrogen (AR inhibitors) therapy

The antiandrogen (AR inhibitors) therapy treatments were selected in CM dataset (ATC code starting with L02BB and G03HA01). L02BB antiandrogens (L02BB01 flutamide, L02BB02 nilutamide, L02BB03 bicalutamide, L02BB04 enzalutamide), G03HA antiandrogens plain (G03HA01 cyproterone).

## 9.12 GnRH agonist/antagonist therapy

The GnRH antagonist treatments were selected in CM dataset (ATC code starting with L02AE, H01CA and L02BX).

L02AE Gonadotropin releasing hormone analogues (L02AE01 buserelin, L02AE02 leuprorelin, L02AE03 goserelin, L02AE04 triptorelin, L02AE05 histrelin), H01CA Gonadotropin releasing hormones, L02BX Other hormone antagonists and related agents (L02BX01 abarelix, L02BX02 degarelix, L02BX03 abiraterone (except if used as previous therapy)).

## 9.13 Hormonal therapy

Hormonal therapy will be were selected in CM dataset:

The GnRH antagonist treatments (ATC code starting with L02AE, H01CA and L02BX).

L02AE Gonadotropin releasing hormone analogues (L02AE01 buserelin, L02AE02 leuprorelin, L02AE03 goserelin, L02AE04 triptorelin, L02AE05 histrelin), H01CA Gonadotropin releasing hormones, L02BX Other hormone antagonists and related agents (L02BX01 abarelix, L02BX02 degarelix, L02BX03 abiraterone (except if used as previous therapy)).

The antiandrogen (AR inhibitors) therapy treatments (ATC code starting with L02BB and G03HA01).

L02BB antiandrogens (L02BB01 flutamide, L02BB02 nilutamide, L02BB03 bicalutamide, L02BB04 enzalutamide), G03HA antiandrogens plain (G03HA01 cyproterone).

#### **9.14 Bone sparing agent**

Bone sparing agent will be were selected in CM dataset, using ATC codes:

M05B drugs affecting bone structure and mineralization, A11CC Vitamin D and analogues, A12A Calcium, A12CD Fluoride, H05BA Calcitonins.
